7 INVESTIGATIONAL PLAN

7.1 Study Design

This will be a prospective, randomized, [REDACTED] controlled, double-masked, parallel-group, daily wear clinical study.

This clinical study will engage approximately 14-17 clinic sites to enroll approximately 252 subjects with approximately 15-21 subjects per site.

Subjects will be expected to attend 4 office visits: Screening / Baseline / Dispense, Week 1 Follow-up, Month 1 Follow-up, and Month 3 Follow up / Exit. The total expected duration of participation for each subject is approximately 3 months in this daily wear study. Subjects will be randomized to wear either the test [REDACTED] contact lenses in both eyes or the control Biofinity contact lenses in both eyes.

Following randomization, study lenses will be dispensed to the subject. [REDACTED]

[REDACTED]

[REDACTED]

[REDACTED]

[figure not shown]
Subjects will wear the lenses while awake in a daily wear modality. CLEAR CARE will be used for daily cleaning and disinfection. [REDACTED]

[REDACTED]

[REDACTED]

Figure 7-1 Flowchart of Study Visits

7.4 Rationale for Choice of Control Product

The Biofinity contact lens was chosen as the control product because this lens is a proper device to compare to [redacted] contact lens with regard to effectiveness and safety. Both the [redacted] contact lens and Biofinity contact lens are frequent replacement SiHy lenses and are to be prescribed for daily wear. The Biofinity contact lenses are indicated for the optical correction of refractive ametropia (myopia and hyperopia) in phakic or aphakic persons with

non-diseased eyes. The lenses are intended to be cleaned and disinfected daily when worn for daily wear and replaced monthly.

7.5 Data Monitoring Committee

Not Applicable

8 STUDY POPULATION

The study population consists of adult male or female subjects (aged 18 or over), with non-diseased eyes, who require optical correction for refractive ametropia. [REDACTED]

The intended study population consists of volunteer subjects who are frequent replacement daily wear soft contact lens wearers, excluding Biofinity habitual wearers, who have at least 3 months of contact lens wearing experience, and who wear their habitual lenses at least 5 days per week and 8 hours per day.

8.1 Inclusion Criteria

Written informed consent must be obtained before any study specific assessment is performed. Upon signing informed consent, the subject will be considered enrolled in the study.

Subjects eligible for inclusion in this study must fulfill **all** of the following criteria:

1. Subject must be at least 18 years of age.
2. Subject must be able to understand and sign an IRB/IEC approved Informed Consent form.
3. Willing and able to attend all scheduled study visits and wear the assigned study lenses as required per protocol.

[Redacted]

[Redacted]

[Redacted]

[Redacted]

[Redacted]

[Redacted]

[Redacted]

[Redacted]

11. Wearing habitual contact lenses in an extended wear modality (routinely sleeping in lenses for at least 1 night per week) over the last 3 months prior to enrollment.

[Redacted]

13. Monovision wearers.

[Redacted]

[Redacted]

[Redacted]

17. Any habitual wear of Biofinity lenses.

[REDACTED]

[REDACTED]

[REDACTED]

Women of childbearing potential or women who are pregnant at the time of study entry are not excluded from participation. [REDACTED]

[REDACTED]

[REDACTED]

[REDACTED]

8.3 Rescreening of Subjects

Rescreening of subjects is not allowed in this study.

9 TREATMENTS ADMINISTERED

9.1 Investigational Product(s)

Test Product(s): [REDACTED] soft contact lenses

Control Product(s) (If applicable): CooperVision® BIOFINITY® (comfilcon A) soft contact lenses

Table 9-1 Test Product

Test Product	[REDACTED] soft contact lenses [REDACTED] (LID015385)
Manufacturer	Alcon Vision, LLC [name] [name] USA
Indication for use and intended purpose in the current study	The intended use of this contact lens is for vision correction.

[Redacted]
	
■ [Redacted]■ [Redacted]■ [Redacted]■ [Redacted]■ [Redacted]■ [Redacted]

[Redacted]
	
[Redacted]

Usage
	
• Wear:
○ Daily Wear
▪ During waking hours only.
■ [Redacted]○ Bilateral• Exposure: At least ~8 hours per day and ~5 days per week over a ~3-month exposure period.
■ [Redacted]• Lens Care/Accessories: CLEAR CARE (mandatory) ■ [Redacted]
■ [Redacted]

[Redacted]
	
[Redacted]

Packaging description	Blister foil pack
-----------------------	-------------------

[figure not shown]
[figure not shown]

[figure not shown]
Table 9-2 Control Product

[figure not shown]
Control Product(s)	Biofinity (comfilcon A) soft contact lenses (Biofinity contact lens) (LID010221)
Manufacturer	CooperVision
Indication for Use	The intended use of this contact lens is for vision correction.
Product description and parameters available for this study	
 • Material: comfilcon A • Water content: 48% • [REDACTED] • Base curve: 8.6 mm (target) • Diameter: 14.0 mm (target)
Formulation	Silicone Hydrogel. Additional details can be found in the Biofinity package insert.
Usage	
 • Wear: 
 ○ Daily Wear 
 ▪ During waking hours only. • [REDACTED] ○ Bilateral • Exposure: At least ~8 hours per day and ~5 days per week over a ~3-month exposure period.

	
[REDACTED]
 
[REDACTED]
 
• Lens Care/Accessories: CLEAR CARE (mandatory) [REDACTED] 
[REDACTED]

--	--

Packaging description	Blister foil pack.
-----------------------	--------------------

More information on the test product can be found in the IB; information on the control product can be found in the Package Insert.

[Redacted]

[Redacted]

9.3 Treatment Assignment / Randomization

Subjects will be randomized in a 2:1 manner to receive either the [Redacted] or Biofinity contact lenses, respectively. [Redacted]

[Redacted]

[Redacted]

[REDACTED]

At Visit 1, all eligible subjects will be randomized [REDACTED] to one of the treatment arms. [REDACTED]

[figure not shown]
[REDACTED]

[figure not shown]
9.4 Treatment Masking

This study is double-masked, with subjects randomized to use [REDACTED] or Biofinity contact lenses for the duration of the 3-month treatment period. [REDACTED]

[figure not shown]
[REDACTED]

[REDACTED]

9.5 Accountability Procedures

It is the Investigator's responsibility to ensure that:

- All study products are accounted for and not used in any unauthorized manner
█ [REDACTED]
- All unused products are available for return to the Study Sponsor, as directed
- Any study lenses associated with a device deficiency or with any product-related AE (ie, ADE or SADE) are returned to the Study Sponsor for investigation, unless otherwise directed by the Sponsor. Refer to Section 11 of this protocol for additional information on the reporting of device deficiencies and AEs [REDACTED]
[REDACTED]

The Investigator is responsible for proper disposition of all unused IPs at the conclusion of the study, [REDACTED]

9.6 Changes to Concomitant Medications, Treatments/ Procedures

After the subject is enrolled into the study, the Investigator must instruct the subject to notify the study site about:

- Any new medications
- Alterations in dose or dose schedules for current medications,
- Any medical procedure or hospitalization that occurred or is planned
- Any non-drug therapies (including physical therapy and blood transfusions).

The Investigator must document this information in the subject’s case history source documents.

10 STUDY PROCEDURES AND ASSESSMENTS

Subjects will be expected to attend 4 office visits, as shown below.

Visit #	Visit Type	Visit Day	Visit Window
Visit 1	Screening / Baseline / Dispense	Day 1	N/A
Visit 2	Week 1 Follow-up Visit	Day 7	[REDACTED]
Visit 3	Month 1 Follow-up Visit	Day 30	[REDACTED]
Visit 4	Month 3 Follow-up / Exit Visit	Day 95	[REDACTED]

[REDACTED]

[REDACTED]

[REDACTED]

[REDACTED]

[REDACTED]

[REDACTED]

[REDACTED]

[REDACTED]

[REDACTED]

[REDACTED]

[REDACTED]

[REDACTED]

[REDACTED] Investigator will complete the order forms for each subject enrolled in this clinical study.

At the Screening / Baseline / Dispense Visit, study lenses will be dispensed to the subject. All subjects will wear the study lenses in a daily wear modality, only during waking hours.

[REDACTED]

[REDACTED]

10.1 Informed Consent and Screening

The Investigator or delegate must explain the purpose and nature of the study, and have the subject read, sign, and date the IRB/IEC-approved informed consent document. The subject must sign the ICF BEFORE any study-specific procedures or assessments can be performed, including study-specific screening procedures. Additionally, have the individual obtaining consent from the subject and a witness, if applicable, sign and date the informed consent document.

The Investigator or delegate must provide a copy of the signed document to the subject and place the original signed document in the subject's chart, or provide documentation as required by local regulations.

10.2 Description of Study Procedures and Assessments

[REDACTED]. The Investigator is responsible for ensuring responsibilities for all procedures and assessments are delegated to appropriately qualified site personnel.

10.2.1 Demographics

Obtain demographic information including age, race, ethnicity, and sex.

10.2.2 Medical History and Concomitant Medications

Collect medical history information, including information on all medications used within the past 30 days. Include herbal therapies, vitamins, and all over-the-counter as well as prescription medications. Throughout the subject's participation, obtain information on any changes in medical health and/or the use of concomitant medications.

10.2.3 Investigational Product Compliance

Review subject compliance with the study lenses usage [REDACTED]

10.2.4 Adverse Event Collection: Safety Assessment

Assess and record any AEs that are observed or reported, including those associated with changes in concomitant medication dosing since the previous visit. Requirements for reporting AEs in the study can be found in Section 11.

10.2.5 Slit-Lamp Biomicroscopy: Safety Assessment

Slit-lamp examination of the cornea, iris/anterior chamber, and lens must be performed in both eyes before instillation of any diagnostic eye drops.

10.2.6 Device Deficiencies: Safety Assessment

Assess and record any device deficiencies that are reported or observed since the previous visit. Requirements for reporting device deficiencies in the study can be found in Section 11.

[REDACTED]

[REDACTED]

[REDACTED]

[REDACTED]

[REDACTED]

[REDACTED]

[REDACTED]

- | [REDACTED]
- | [REDACTED]
- | [REDACTED]
- | [REDACTED]
- | [REDACTED]
- | [REDACTED]
- | [REDACTED]
- | [REDACTED]
- | [REDACTED]
- | [REDACTED]
- | [REDACTED]
- | [REDACTED]
- | [REDACTED]
- | [REDACTED]
- | [REDACTED]

[REDACTED]

[REDACTED]

10.4 Discontinued Subjects

10.4.1 Screen Failures

Screen failures are subjects who were excluded from the study after signing the informed consent, not meeting the inclusion/exclusion criteria, and prior to randomization to product/dispense of study product.

The Investigator must document the reason for screen failure in the subject's case history source documents.

Subject numbers must not be re-used.

10.4.2 Discontinuations

Discontinued subjects are individuals who voluntarily withdraw or are withdrawn from the study by the Investigator after signing the informed consent.

Subject numbers of discontinued subjects must not be re-used.

Subjects may discontinue from study or study treatment at any time for any reason. Subjects may also be discontinued from study treatment at any time if, in the opinion of the Investigator, continued treatment poses a risk to their health.

[Redacted text block]

[Redacted text block]

[Redacted text block]

[Redacted text block]

[Redacted text block]

10.5 Clinical Study Termination

The Study Sponsor reserves the right to close the investigational site or terminate the study in its entirety at any time.

If the clinical study is prematurely terminated or suspended by the Study Sponsor:

- The Study Sponsor must:
 - Immediately notify the Investigator(s) and subsequently provide instructions for study termination.
 - Inform the Investigator and the regulatory authorities of the termination/suspension and the reason(s) for the termination/suspension.

- The Investigator must:
 - Promptly notify the IRB/IEC of the termination or suspension and of the reasons.
 - Provide subjects with recommendations for post-study treatment options as needed.

The Investigator may terminate the site’s participation in the study for reasonable cause.

10.5.1 Follow-Up of Subjects After Study Participation Has Ended

Study visits are not a substitute for routine eye care. Following this study, the subject will return to their eye care professional for their routine eye care.

11 ADVERSE EVENTS AND DEVICE DEFICIENCIES

11.1 General Information

An AE is any untoward medical occurrence, unintended disease or injury, or untoward clinical signs (including abnormal laboratory findings) in subjects, users, or other persons, whether or not related to the investigational medical device (test article). Refer to the Glossary of Terms and figures below for categories of AEs and SAEs.

Figure 11–1 Categorization of All AEs

[figure not shown]
[figure not shown]

Figure 11–2 Categorization of All SAE

SAEs

In addition to reporting all AEs (serious and non-serious) meeting the definitions, the Investigator must report any occurrence of the following as an SAE:

- An ocular infection including a presumed infectious ulcer with any of the following characteristics:
 - Central or paracentral location
 - Penetration of Bowman’s membrane
 - Infiltrates > 2 mm diameter
 - Iritis
 - Increase in intraocular pressure
 - Culture positive for microorganisms
 - Increasing size or severity at subsequent visits
- Any central or paracentral corneal event (such as neovascularization) that results in permanent opacification

- Hypopyon
- Hyphema
- Neovascularization within the central 6 mm of the cornea
- Permanent vision loss as defined by loss of 2 or more lines of BCVA from enrollment visit that fails to resolve
- Uveitis (anterior, intermediate, or posterior)
- Corneal abrasion affecting $\geq 50\%$ of corneal surface area

Significant Non-Serious AE

A significant non-serious AE is a device-related, non-sight threatening AE that warrants discontinuation of any contact lens wear for greater than or equal to 2 weeks. In addition, the Investigator must report any occurrence of the following as a Significant Non-Serious Adverse Event:

- Peripheral non-progressive non-infectious ulcers
- All symptomatic corneal infiltrative events
- Corneal staining score greater than or equal to Grade 3 [REDACTED]
- Temporary vision loss as defined by loss of 2 or more lines of BCVA from enrollment visit that persists for 2 or more weeks
- Neovascularization score greater than or equal to Grade 2 [REDACTED]

[REDACTED]

Device Deficiencies

A device deficiency is inadequacy of a medical device with respect to its identity, quality, durability, reliability, safety, or performance. A device deficiency may or may not be associated with subject harm (ie, ADE or SADE); however, not all ADEs or SADEs are due to a device deficiency. The Investigator should determine the applicable category listed in the Device Deficiency eCRF for the identified or suspect device deficiency and report any subject harm separately. Examples of device deficiencies include the following:

- Failure to meet product specifications (eg, incorrect lens power/diameter/base curve/color)
- Lens cloudy
- Lens surface/edge defect
- Torn lens during handling/in pack
- Packaging deficit (eg, mislabeled product)
- Suspect product contamination
- Lack of performance

11.2 Monitoring for AEs

At each visit, after the subject has had the opportunity to spontaneously mention any problems, the Investigator should inquire about AEs by asking the standard questions:

- “Have you had any health problems since your last study visit?”
- “Have there been any changes in the medicines you take since your last study visit?”

[REDACTED]

[REDACTED]

[REDACTED]

[REDACTED]

[REDACTED]

11.3 Procedures for Recording and Reporting

AEs are collected from the time of informed consent. Any pre-existing medical conditions or signs/symptoms present in a subject prior to the start of the study (ie, before informed consent is signed) are not considered AEs in the study and should be recorded in the Medical History section of the eCRF.

[figure not shown]
[REDACTED]

[REDACTED]

[REDACTED]

For each recorded event, the ADEs and SAEs documentation must include: date of occurrence, severity, treatment (if applicable), outcome, and assessments of the seriousness and causality. In addition, the Investigator must document all device deficiencies reported or observed with test and control products on the Device Deficiency eCRF.

- ADEs or SAEs are documented on the *Serious Adverse Event and Adverse Device Effect* eCRF within 24 hours of the Investigator's or site's awareness.
- Device deficiencies are documented on the *Device Deficiency* eCRF within 24 hours of the Investigator's or site's awareness.
- A printed copy of the completed *Serious Adverse Event and Adverse Device Effect* and/or *Device Deficiency* eCRF must be included with product returns.
- Additional relevant information after initial reporting must be entered into the eCRF as soon as the data become available.
- Document any changes to concomitant medications on the appropriate eCRFs.
- Document all relevant information from Discharge Summary, Autopsy Report, Certificate of Death, etc, if applicable, in narrative section of the *Serious Adverse Event and Adverse Device Effect* eCRF.

Intensity and Causality Assessments

Where appropriate, the Investigator must assess the intensity (severity) of the AE based upon medical judgment with consideration of any subjective symptom(s), as defined below:

Intensity (Severity)

Mild An AE is mild if the subject is aware of but can easily tolerate the sign or symptom.

Moderate An AE is moderate if the sign or symptom results in discomfort significant enough to cause interference with the subject's usual activities.

[figure not shown]
Severe An AE is severe if the sign or symptom is incapacitating and results in the subject's inability to work or engage in their usual activities.

For every AE in the study, the Investigator must assess the causality (Related or Not Related to the medical device or study procedure). An assessment of causality will also be performed by Study Sponsor utilizing the same definitions, as shown below:

Causality

Related An AE classified as related may be either definitely related or possibly related where a direct cause and effect relationship with the medical device or study procedure has not been demonstrated, but there is a reasonable possibility that the AE was caused by the medical device or study procedure.

Not Related An AE classified as not related may either be definitely unrelated or simply unlikely to be related (ie, there are other more likely causes for the AE).

11.5 Unmasking of the Study Treatment

Masked information on the identity of the assigned medical device should not be disclosed during the study. [REDACTED]

[REDACTED]

11.6 Follow-Up of Subjects with AEs

The Investigator is responsible for adequate and safe medical care of subjects during the study and for ensuring that appropriate medical care and relevant follow-up procedures are maintained after the study.

[REDACTED]

[REDACTED]

[REDACTED]

11.7 Pregnancy in the Clinical Study

Women of childbearing potential or women who are pregnant at the time of study entry are not excluded from participation. [REDACTED]

[REDACTED]

12 ANALYSIS PLAN

Data from a subset of subjects in the CLL949-C009 study will be combined with data from this study. This combined set will serve as the basis for all analyses detailed in this section. Subjects in CLL949-C009 will be included in the combined set only if they satisfy the following criterion:

- BCVA of 20/20 or better in each eye at the Screening / Baseline / Dispense Visit

[REDACTED]

[REDACTED]

[REDACTED]

[REDACTED]

[REDACTED]

[REDACTED]

[REDACTED]

[REDACTED]

12.1 Subject Evaluability

Final subject evaluability must be determined prior to breaking the code for masked treatment (lens) assignment and locking the database, based upon the Deviations and Evaluability Plan (DEP).

12.2 Analysis Sets

12.2.1 Safety Analysis Set

Safety analyses will be conducted using the safety analysis set on a treatment-emergent basis. As such, the safety analysis set will include all subjects/eyes exposed to any study lenses evaluated in this study, [REDACTED]

[REDACTED] For treatment-emergent safety analyses, subjects/eyes will be categorized under the actual study lenses exposed.

12.2.2 Full Analysis Set

The full analysis set (FAS) is the set of all randomized subjects who are exposed to any study lenses evaluated in this [REDACTED], and who have at least one post-baseline (post-Dispense) CLCDVA.

12.2.3 Per Protocol Analysis Set

The per protocol (PP) analysis set is a subset of FAS and excludes all data/subjects that have met any of the critical deviation or evaluability criteria identified in the DEP.

12.3 Demographic and Baseline Characteristics

Demographic information, recent lens-wearing experience (including wear modality and wear success), and habitual lens information will be presented by lens group and overall. Counts and percentages will be presented for categorical variables such as sex, age group, race, an ethnicity. Number of observations, mean, SD, median, minimum, and maximum will be presented for continuous variables such as age.

12.4 Effectiveness Analyses

[Redacted text block]

[Redacted text block]

12.4.1 Analysis of Primary Effectiveness Endpoint(s)

The primary effectiveness objective is to demonstrate noninferiority [Redacted] compared to Biofinity in mean CLCDVA at Week 1 Follow-up.

The primary endpoint is the mean CLCDVA at Week 1 Follow-up. The corresponding assessment is collected with study lenses, in Snellen, for each eye. Conversion will be made to the logMAR scale.

12.4.1.1 Statistical Hypotheses

The null and alternative hypotheses are formulated in terms of the predefined margin of 0.10 (in logMAR scale) for noninferiority:

$$H_0: \mu_{(T)} - \mu_{(C)} \geq 0.10$$

$$H_a: \mu_{(T)} - \mu_{(C)} < 0.10$$

where $\mu_{(T)}$ and $\mu_{(C)}$ denote the Week 1 Follow-up mean CLCDVA for [REDACTED] and Biofinity contact lenses, respectively, on the logMAR scale.

12.4.1.2 Analysis Methods

A mixed effects repeated measures model will be utilized to test these hypotheses. The model will include terms for lens, visit (Dispense, Week 1 Follow-up, Month 1 Follow-up, and Month 3 Follow-up), and lens-by-visit interaction as fixed effects, protocol as a random effect and baseline best corrected distance VA as a covariate. Within-subject correlation due to eye will also be accounted for in the model. Lens difference ([REDACTED] minus Biofinity) and the corresponding two-sided 95% CI will be computed for 1-Week Follow-up. Noninferiority in CLCDA will be declared if the upper confidence limit is less than 0.10.

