Study Design	
This will be a prospective, randomized, [REDACTED] [REDACTED] controlled, double-masked, parallel-group, daily wear clinical study. Subject participation in the study will be approximately 14 weeks with approximately 3 months of exposure to study lenses.

Subject population	
Volunteer subjects aged 18 or over who are adapted daily wear frequent replacement soft contact lens wearers, excluding Biofinity habitual wearers, have at least 3 months of soft contact lens wearing experience, and who wear their habitual lenses at least 5 days per week and at least 8 hours per day.
 
[REDACTED]
 
[REDACTED]

Key inclusion criteria (See Section 8.1 for a complete list of inclusion criteria)	
 • Successful wear of spherical daily wear frequent replacement soft contact lenses for distance correction in both eyes during the past 3 months for a minimum of 5 days per week and 8 hours per day. • Manifest cylinder ≤ 0.75 D in each eye. • Best spectacle corrected visual acuity 20/20 or better in each eye. 
█ [REDACTED]
 
[REDACTED]

Table 3-1 Schedule of Study Procedures and Assessments

Procedure/ Assessment	Visit 1	Visit 2	Visit 3	Visit 4	Early Exit	USV
	Screening/ Baseline/ Dispense Day 1	Week 1 Follow-up Day 7	Month 1 Follow-up Day 30	Month 3 Follow-up/ Exit Day 95		
Informed Consent	✓	-	-	-	-	-
Demographics	✓	-	-	-	-	-
Medical History	✓	✓	✓	✓	✓	(✓)
Concomitant Medications	✓	✓	✓	✓	✓	(✓)
Inclusion/ Exclusion	✓	-	-	-	-	-
Habitual lens information (brand / manufacturer, modality, power, wear success, habitual lens care brand)	✓	-	-	-	-	-
[REDACTED]	■	■	■	■	■	■
[REDACTED]	■	■	■	■	■	■
[REDACTED]	■	■	■	■	■	■
[REDACTED]	■	■	■	■	■	■
[REDACTED]	■	■	■	■	■	■
[REDACTED]	■	■	■	■	■	■
Biomicroscopy ²	✓	✓	✓	✓	✓	(✓)
[REDACTED]	■	■	■	■	■	■
[REDACTED]	■	■	■	■	■	■
[REDACTED]	■	■	■	■	■	■
[REDACTED]	■	■	■	■	■	■
Randomize	✓	-	-	-	-	-
[REDACTED]	■	■	■	■	■	■

[Redacted]

[Redacted]

[Redacted]

[Redacted]

[Redacted]

[Redacted]

[Redacted]

[Redacted]

[Redacted]

[Redacted]

[Redacted]

[Redacted]

[Redacted]

[Redacted]

[Redacted]

[Redacted]

[Redacted]

[Redacted]

[Redacted]

[Redacted]

[Redacted]

[Redacted]

[figure not shown]
[Redacted]

[Redacted]

[Redacted]

[Redacted]

[Redacted]

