1.2 Study Description

Key components of the study are summarized in Table 1-1.

Table 1-1 Study Description Summary

Study Design	Prospective, multi-center, randomized, [REDACTED], controlled, double-masked, parallel-group
Study Population	Volunteer subjects aged 18 or over who are adapted daily wear frequent replacement soft contact lens wearers, excluding Biofinity habitual wearers, have at least 3 months of soft contact lens wearing experience, and who wear their habitual lenses at least 5 days per week and at least 8 hours per day. [REDACTED] [REDACTED] [REDACTED] [REDACTED] [REDACTED] [REDACTED]

	Target to complete: 192 subjects (128:64; Test:Control) [REDACTED] [REDACTED] [REDACTED] Planned: ~252 subjects enrolled, ~228 subjects randomized (152:76; Test:Control)
Number of Sites	~14-17 (US)
Test Product	[REDACTED] soft contact lenses [REDACTED]
Control Product	CooperVision® BIOFINITY® (comfilcon A) soft contact lenses (Biofinity)
Duration of Treatment	Approximately 3 months
Visits	Visit 1: Screening/Baseline/Dispense (Day 1) Visit 2: Week 1 Follow-up [REDACTED] Visit 3: Month 1 Follow-up [REDACTED] Visit 4: Month 3 Follow-up/Exit [REDACTED]

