1.4 Masking

This study is double-masked.

[REDACTED]

[REDACTED]

[REDACTED]

2 Analysis Sets

Data from a subset of subjects in the CLL949-C009 study will be combined with data from this study. This combined set will serve as the basis for all analyses for the primary and secondary effectiveness objectives. Subjects in CLL949-C009 will be included in the combined set only if they satisfy the following criterion:

- Best corrected visual acuity (BCVA) of 20/20 or better in each eye at the Screening / Baseline / Dispense Visit

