2.3 Per Protocol Analysis Set

The per protocol (PP) analysis set is a subset of FAS and excludes all data/subjects that have met any of the critical deviation or evaluability criteria identified in the Deviations and Evaluability Plan (DEP).

3 Subject Characteristics and Study Conduct Summaries

Demographic information (age, sex, ethnicity, and race), recent lens-wearing experience (wear modality, wear success), and habitual lens information will be presented by lens group and overall for the safety, full, and per protocol analysis sets.

Baseline data will also be summarized by lens group and overall on the safety, full and per protocol analysis sets.

[REDACTED]

- [REDACTED]
- [REDACTED]
- [REDACTED]
- [REDACTED]
- [REDACTED]
- [REDACTED]
- [REDACTED]
- [REDACTED]

4 Effectiveness Analysis Strategy

[REDACTED]

[REDACTED]

[REDACTED] Primary inference will be done on the PP analysis set. [REDACTED]

[REDACTED]

[REDACTED]

[REDACTED]

[REDACTED]

[REDACTED]

[REDACTED]

[REDACTED]

[REDACTED].

All data obtained in evaluable subjects/eyes will be included in the analysis. No imputation for missing values will be carried out for the effectiveness analyses.

For all planned inferential analyses, alternative models/methods may be considered if convergence cannot be achieved.

[figure not shown]

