5.3.3 Device Deficiencies

A frequency table showing counts for each treatment-emergent Device Deficiency category will be presented. In addition, listings for treatment-emergent and pre-treatment device deficiencies will be provided.

[REDACTED]

[figure not shown]

[figure not shown]

9 References

1. ISO 11980:2012 Ophthalmic optics - Contact lenses and contact lens care products - Guidance for clinical investigations

[figure not shown]

11 Appendix

[figure not shown]
Table 11-1 Schedule of Study Procedures and Assessments

Procedure/ Assessment	Visit 1	Visit 2	Visit 3	Visit 4	Early Exit	USV
	Screening/ Baseline/ Dispense	Week 1 Follow-up	Month 1 Follow-up	Month 3 Follow-up/ Exit		
	Day 1	Day 7	Day 30	Day 95		
Informed Consent	✓	-	-	-	-	-
Demographics	✓	-	-	-	-	-
Medical History	✓	✓	✓	✓	✓	(✓)
Concomitant Medications	✓	✓	✓	✓	✓	(✓)
Inclusion/ Exclusion	✓	-	-	-	-	-
Habitual lens information (brand / manufacturer, modality, power, wear success, habitual lens care brand)	✓	-	-	-	-	-
VA w/ habitual correction (OD,OS Snellen distance)	✓	-	-	✓	✓	(✓)
[REDACTED]	■	■	■	■	■	■
[REDACTED]	■	■	■	■	■	■
[REDACTED]	■	■	■	■	■	■
[REDACTED]	■	■	■	■	■	■
[REDACTED]	■	■	■	■	■	■
Biomicroscopy ²	✓	✓	✓	✓	✓	(✓)
[REDACTED]	■	■	■	■	■	■
[REDACTED]	■	■	■	■	■	■

[figure not shown]
Procedure/ Assessment	Visit 1	Visit 2	Visit 3	Visit 4	Early Exit	USV
	Screening/ Baseline/ Dispense Day 1	Week 1 Follow-up Day 7	Month 1 Follow-up Day 30	Month 3 Follow-up/ Exit Day 95		
[REDACTED]	■	■	■	■	■	■
Randomize	✓	-	-	-	-	-
[REDACTED]	■	■	■	■	■	■
IP Dispense	✓	✓	(✓)	-	-	(✓)
VA w/ study lenses (OD, OS Snellen distance)	✓	✓	✓	✓	✓	(✓)

Procedure/ Assessment	Visit 1	Visit 2	Visit 3	Visit 4	Early Exit	USV
	Screening/ Baseline/ Dispense	Week 1 Follow-up	Month 1 Follow-up	Month 3 Follow-up/ Exit		
	Day 1	Day 7	Day 30	Day 95		

AEs	✓	✓	✓	✓	✓	(✓)
Device deficiencies	✓	✓	✓	✓	✓	(✓)
Exit Form	(✓)	(✓)	(✓)	✓	✓	(✓)

Additional Notes:

- a) All follow-up visits should be scheduled **at least 4 hours after lens insertion** ([redacted]
[redacted]
[redacted]
[redacted]

Signature Page for V-CLN-0002343 v2.0

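### Does leaving habitual-correction acuity and site out of the primary model cost the trial precision that it needs?

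*Protocol*

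**What the plan says.** Protocol Section 12.4.1.2 names the terms of the primary model: lens, visit and lens-by-visit as fixed effects, protocol as a random effect, and "baseline best corrected distance VA as a covariate". Correlation between a subject's two eyes is also modelled. Noninferiority is declared if the upper limit of the two-sided 95% CI at Week 1 lies below 0.10 logMAR. In SAP Section 4.3.1 the text after the opening sentence on the model is redacted, so only the protocol's list can be judged.

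The covariate is restricted in both data sources. The key inclusion criteria in Protocol Section 3 require "Best spectacle corrected visual acuity 20/20 or better in each eye". Protocol Section 12 and SAP Section 2 admit C009 subjects only with "BCVA of 20/20 or better in each eye at the Screening / Baseline / Dispense Visit".

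Two other candidate terms exist in this study. SAP Table 11-1 schedules "VA w/ habitual correction (OD,OS Snellen distance") at Visit 1, and Protocol Section 7.1 states: "This clinical study will engage approximately 14-17 clinic sites to enroll approximately 252 subjects with approximately 15-21 subjects per site". The sample size line in SAP Table 1-1 reads "Target to complete: 192 subjects (128:64; Test:Control"). All primary and secondary effectiveness analyses use the pooled C009 and C018 data.

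**The concern.** A baseline covariate earns its place by explaining outcome variance, and cutting its range weakens it. Here the only baseline covariate is cut at 20/20 on the poor side in every analysed subject. A second baseline acuity measure, same eye and same Snellen chart, has no visible cap and is already scheduled. Acuity is also read by staff at many sites, so some variance between sites is plausible. If randomization was balanced within site, a model without site reports an SE larger than the true sampling variability.

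At stake is precision: a CI wider than the collected data allow and, in an unfavourable case, a lens that is noninferior but not shown to be so. Bias is not at stake, because allocation is randomized. Nor is the type I error rate inflated, because an overstated SE makes noninferiority harder to claim.

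**Working it through.** **Inputs.** From the documents: 128 test and 64 control completers, margin 0.10, two-sided 95% CI, both eyes on the same lens. No SD, inter-eye correlation, covariate correlation or site ICC is visible, so all of these are assumptions. There is also no stated precision or power figure to reproduce.

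**1. Half-width without the extra terms (C018 alone, one visit).**

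Half-width = t(0.975, 190) × SD × √[(1+ρ)/2 × (1/128 + 1/64)], with ρ the inter-eye correlation, assumed 0.7.

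- SD 0.10: SE = 0.10 × √(0.85 × 0.02344) = 0.0141; half-width 0.0278.
- SD 0.15: half-width 0.0418.

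With one value per subject and a normal quantile, 1.96 × SD × √(1/128 + 1/64) = 1.96 × SD × 0.1531. This gives 0.0300 at SD 0.10 and 0.0600 at SD 0.20. At an observed difference of zero, the upper limit reaches 0.10 only when SD = 0.10/(1.96 × 0.1531) ≈ 0.33.

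**2. Gain under assumed correlations.** A subject-level partial correlation r beyond BCVA multiplies the SE by √(1−r²). A site ICC with allocation balanced within site multiplies it by √(1−ICC).

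| Assumption | Factor | Half-width, SD 0.10 | Half-width, SD 0.15 |
|---|---|---|---|
| none | 1 | 0.0278 | 0.0418 |
| r = 0.3, ICC = 0.05 | √(0.91 × 0.95) = 0.930 | 0.0259 | 0.0388 |
| r = 0.5, ICC = 0.15 | √(0.75 × 0.85) = 0.798 | 0.0222 | 0.0333 |

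Even in the last row, and ignoring any shift in the estimate, the decision changes only for an observed difference between 0.1000 − 0.0278 = 0.0722 and 0.1000 − 0.0222 = 0.0778 at SD 0.10. At SD 0.15 the window is 0.0582 to 0.0667.

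**3. Is the direction of the gain established?** In one simulation, 192 subjects at 16 sites were randomized without balance within site. BCVA was truncated at logMAR 0, its slope was 0.6 and the residual SD was 0.08.

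| Slope of habitual acuity | Site ICC | CI change, habitual acuity added | CI change, 16 fixed site effects added as well |
|---|---|---|---|
| 0 | 0 | +0.3% | +4.3% |
| 0 | 0.10 | +0.3% | −0.4% |
| 0.3 | 0 | −0.9% | +3.3% |
| 0.3 | 0.10 | −0.8% | −1.7% |
| 0.6 | 0 | −4.2% | −0.1% |
| 0.6 | 0.10 | −3.5% | −4.4% |

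A second simulation, with an exact 8:4 split in each of 16 sites, gave SE reductions of 6.7% (r = 0.3, ICC 0.05) and 19.4% (r = 0.5, ICC 0.15). With r = 0 and ICC = 0 the SE rose 0.2%, or 4.5% if allocation was not balanced by site. The sign and size follow from the assumptions, not from anything in the documents.

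**4. Power with a true difference of 0 (one value per subject).** Power = Φ(0.10/SE − 1.96). At SD 0.15, SE = 0.15 × 0.1531 = 0.0230 and power = Φ(4.355 − 1.96) = 99.2%. It is above 99.9% at SD 0.10, 90.4% at 0.20 and 74.3% at 0.25. Explaining a further 20% of the residual variance raises the last two to 95.5% and 83.2%.

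**The case for a change.** The strongest case for adding the terms has three parts.

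First, precision matters if the test lens is truly somewhat worse. At a true difference of 0.05 and subject-level SD 0.15, power is 58.6%; a further 10% of variance explained gives 63.1%, and 20% gives 68.2%. This stands as arithmetic. But it uses C018 alone, needs a true difference of half the margin, and needs explained variance that no document supports. Habitual acuity may itself sit near ceiling: these are successful wearers with cylinder of at most 0.75 D and best corrected acuity of 20/20 or better.

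Second, if allocation was balanced within site, omitting site overstates the SE: in simulation at ICC 0.15, a reported 0.0152 against an empirical 0.0138. This is right in principle. The text that would show such balance is redacted in Protocol Section 9.3 and SAP Section 1.3, and the redacted part of SAP Section 4.3.1 may contain a site term. The effect is also conservative.

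Third, the change looks cheap, since C018 needs no new data. But the primary analysis pools C009, and the documents do not say whether C009 recorded habitual acuity or whether its site data can be used. With no imputation planned, subjects lacking the covariate could drop out of the model and cost precision. Confining the richer model to a C018-only sensitivity analysis leaves the primary CI exactly as it is. Site nested within a two-level protocol effect adds convergence risk, and SAP Section 4 already allows that "alternative models/methods may be considered if convergence cannot be achieved". The simulations used fixed site effects; a random effect should cost less, but that was not computed. If C009 is already unmasked, which is not stated, choosing new primary covariates now would itself draw criticism.

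**Conclusion.** The concern does not hold. The observations behind it are accurate: best corrected acuity is the only baseline covariate in the protocol's list, its range is restricted, and habitual acuity and site are not listed. They do not amount to a fault. The model adjusts for baseline acuity, separates the two studies and handles the paired eyes; a trial need not adjust for every variable it collects. There is no bias, no inflated type I error and no contradiction between the documents.

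At assumed eye-level SDs of 0.10 to 0.15 the half-width is 0.028 to 0.042 against a margin of 0.10, before C009 is added, so the noninferiority decision is unlikely to turn on this choice. It could matter at a subject-level SD of about 0.20 or more, or with a true difference well above zero; the documents give no sign of either. The size of any gain, and even its sign once site is added, depends on assumed correlations, ICCs and within-site balance. Adding the terms is a debatable preference. All half-widths and power figures are single-visit approximations to the planned mixed model, based on C018 completers alone.
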